## **Mixed Methods Evaluation of Implementation Outcomes**

---

We will conduct secondary analyses to understand patient-level (age, sex, race, insurance, etc.), clinician/health system-level (academic/non-academic, urban/rural setting, etc.), and intervention-level (timing of delivery of prompt, etc.) predictors of “success” (prescription of an evidence-based CV risk reduction therapy) by each implementation approach where applicable.

In addition, clinicians engaging with any of the implementation interventions, we will assess use of the technology and referral completion rates to the virtual GDMT team. Specifically, we will attempt to track the following elements:

1. Time from referral order to first appointment in GDMT team
2. Attendance rate GDMT team appointment (patient leakage)
3. Timing from message to new appointments/new messages from provider to patient, which helps determine if this inter-visit time is actually a ‘semi-hot’ state.

We will collect data and assess relative timelines of intervention, clinic visits, and timing of medication prescriptions. This would help us understand if changes in prescription are clustered around the time of the intervention (even in the absence of a scheduled visit) or if visits are scheduled after intervention to discuss therapeutic changes.

Short questionnaires will also be completed by patient participants (See Appendix).

## **Treatment of Patients**

---

All care decisions will be left to the treating clinician, and no care recommendations will be mandated. We will leverage the Biofourmis platform to manage patients and provide referral to a virtual GDMT team.

### **Site based procedures and Study Managers:**

- A) Patient-Level Randomization Stratified by Study Site:** The unit of allocation will be the patient. However, to ensure balance of participants and account for any large baseline variation in care practices across health systems, the analysis will be stratified by study site.
- B) Study Manager:** In quality improvement arm A, Study Managers may facilitate access of CardioSmart materials to the patient. In quality improvement arm B, Study Managers will enroll patients in technology guided care using standardized language. In study arm C, Study Managers will create e-referrals to the virtual GDMT team.
- C) Qualitative Surveys:** The sites will participate with the quality ambassadors in any surveys, including the qualitative survey, and provide regular feedback to the ambassadors for any challenges and/or best practices discovered. In addition, patient participants will

complete a brief baseline assessment of perceptions around care quality, cardiovascular risk, willingness to take another therapy, and therapeutic relationships.

### **Rationale for Selection Criteria**

---

The study was designed to identify patients at risk for cardiovascular events who meet eligibility criteria for treatment optimization for GDMT. The exclusion criteria are employed to minimize potential risks of individuals and reduce the number of patients who may be intolerant or ineligible for therapy.

### **Withdrawal criteria**

---

All PCPs and cardiologists (target clinicians for the quality improvement initiative) will receive a correspondence prior to the start of the study describing the initiative. Any clinician who does not wish to receive the quality improvement communication will be allowed to opt-out such that all patients under their direct care will not be eligible for the study. At any time during the study, clinicians may decide to similarly opt-out. All patients who have already been randomized prior to clinician withdrawal will be analyzed in the originally randomized arm (intention-to-treat approach).

### **Risk/Benefit Assessment**

---

As study procedures reflect CV medication management via guideline recommendations supported by the clinical judgment of the managing physician, there is no envisioned procedural risk to patients through involvement in the study. No testing, time, risk, or procedures beyond those required for routine care will be imposed. The primary risk associated with this project is the potential for a breach of patient confidentiality. The ACCF has established a robust plan for ensuring appropriate and commercially reasonable physical, technical, and administrative safeguards are in place to mitigate such risks as described in the Quality Control section of this protocol.

### **Data Sources**

---

Data sources will be EMR, other data in the technology solution, electronic informed consent forms and patient survey questionnaires administered by the Biofourmis patient app.

### **Statistical Methods**

---

**The final Statistical Analysis Plan (SAP) will be finalized prior to the study completion.**

**Patient-Level Randomization to 3 Quality Improvement Initiative:** Simple (traditional) randomization minimizes variation in clinical profiles of patients included in each arm. While cluster randomization at the clinician level may limit the potential for contamination bias (chance that clinicians caring for patients randomized to one implementation approach may influence the care of another patient on their panel), the number of eligible patients under each individual clinician's care is anticipated to be small.

**Power Estimates:** In this 3-arm trial, stratified by study site, we estimated the sample size of patients needed to show a difference between the quality improvement arms.

Current estimates of use of either SGLT2i or GLP-1RA among eligible patients is 15%. Assuming an alpha of 0.05, we would require 121 patients in each of the 3 arms to show 80% power to detect at least an absolute difference of 15% between education alone and the education + decision support arms and a 15% between education alone and the education + decision support + facilitated referral group. Assuming a 20-25% loss to follow-up rate, 750 patients would be required.

Current estimates of optimal GDMT prescription and titration for HFrEF are 2%. The differences for each arm are expected to be greater than the SGLT2i or GLP-1RA classes.

Given the evolving evidence for HFpEF, there are no established rates for GDMT.

Current estimates of optimal use of anticoagulation medication for AF is 60-65%. The study does not anticipate reaching power for this disease state.

The primary comparison will be between the education alone arm (1) and the education + decision support + referral group (3). Secondary analyses will compare education alone (1) with the education + decision support group (2). The study will be powered for both primary and secondary comparisons for T2D/ASCVD and HF (HFrEF and HFpEF combined).

Rates of Primary Endpoint Over 9 months			Estimated Number of Patients in Each of 3 Arms			
Education Alone (1)	Education +Decision Support (2)	Education+Decision+Referral Support (3)	80% power		90% power	
			1 vs 2	1 vs 3	1 vs 2	1 vs 3
0.05	0.075	0.1	1471	435	1969	582
0.1	0.15	0.2	686	199	918	266
0.125	0.1875	0.25	529	152	708	203
0.15	0.3	0.3	424	121	568	161

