#### **Research Methods**

---

All eligible patients (see detailed inclusion/exclusion criteria above) with HF, AF and/or with T2D/ASCVD, who are not currently treated on optimal GDMT will be identified across all health systems.

All eligible patients will be randomized to 1 of the 3 implementation approaches and remain under the randomized strategy for the remainder of the study (following intention-to-treat principles). Even if the patient changes PCP or cardiologist (expected low frequency), patients will continue to receive the care under the arm in which they were randomized to. The interventions will be clinician-facing and we chose to select PCP and cardiologists as the target for quality improvement for several reasons: 1) PCPs represent a large cohort of clinicians across health systems, serving as the entry of care and access point for specialty referrals; 2) Patients are unlikely to change PCPs and cardiologist during the short-term duration of the study; 3) Most or all patients are assigned a PCP in a health system thus allowing for clear clinician attribution; 4) PCPs and cardiologists may have sufficient exposure and comfort with prescription of these risk reduction therapies to allow successful intervention to action. If patients leave the health system entirely, then the participant will be censored as lost to follow-up.

**Randomization Scheme:** Patients will be randomized 1:1:1 to the 3 quality improvement strategies using a standardized randomization software within the Biofourmis platform. To ensure adequate power, enrollment will only end when all three arms have met their individual targets for

patient accrual in both disease categories and representation of underserved populations and those with health care disparities historically across sites. Enrollment of patients with comorbidities will be accomplished through prospective patient identification of patients eligible by disease state and focus populations.

- A) **Clinician and Patient Education:** This implementation strategy will support engaging the patients with their existing clinicians using a CardioSmart materials to guide treatment expectations. Clinicians also will receive education on the latest medications for CV risk management. There is no “placebo” arm.

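### The protocol describes the allocation scheme inconsistently, and no reading of it balances the disease cohorts on which enrolment stops and power is claimed

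*Protocol*

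**What the plan says.** The protocol describes allocation in four places.

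- **Research Methods, Randomization Scheme.** "Patients will be randomized 1:1:1 to the 3 quality improvement strategies using a standardized randomization software within the Biofourmis platform". No stratification factor is named. The same paragraph sets the stopping rule: "enrollment will only end when all three arms have met their individual targets for" accrual by disease category and by representation of underserved groups. It gives no per-arm numbers.
- **Site based procedures and Study Managers, item A.** The heading is "Patient-Level Randomization Stratified by Study Site". The text makes the patient the unit of allocation, then states an aim and a means in one clause: "ensure balance of participants and account for any large baseline variation in care practices across health systems, the analysis will be stratified by study site".
- **Statistical Methods, paragraph on patient-level randomisation.** "Simple (traditional) randomization minimizes variation in clinical profiles of patients included in each arm". The next sentence discusses cluster randomisation by clinician as the alternative.
- **Statistical Methods, Power Estimates.** "In this 3-arm trial, stratified by study site, we estimated the sample size of patients". Later in this part, power is claimed for T2D/ASCVD and for HFrEF and HFpEF combined.

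The Population section plans 750 patients with overlapping conditions: 250 HFrEF, 250 HFpEF, 500 AF and 250 T2D/ASCVD.

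**The concern.** Simple randomisation and randomisation stratified by site are different methods, and whoever configures the software has to build one of them. The paragraph that should settle the matter, the Randomization Scheme, does not. The site-procedures item also gives a stratified analysis the task of making the arms balanced. Such an analysis can adjust for imbalance after the fact but has no influence on who is allocated where.

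The more practical gap is that disease cohort is not an allocation factor anywhere, whichever description is right. Outcomes are defined separately by disease, and the assumed current rates differ widely (15% for SGLT2i or GLP-1RA use, 2% for optimal HFrEF therapy, 60-65% for anticoagulation in AF). Power is claimed by disease, and accrual closes on per-arm disease counts. If those counts are left to chance, the stopping rule waits for whichever arm happens to lag in whichever cohort. At stake are extra patients, some chance difference in disease mix between arms, and an allocation method that cannot be implemented unambiguously.

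**Working it through.** **1. The descriptions side by side**

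| Place | Allocation | Analysis |
|---|---|---|
| Randomization Scheme | 1:1:1, no factor named | not addressed |
| Site procedures, item A, heading | stratified by site | not addressed |
| Site procedures, item A, text | patient is the unit | stratified by site, to secure balance |
| Statistical Methods, randomisation paragraph | simple | not addressed |
| Power Estimates | trial stratified by site | not addressed |

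None of the five names disease cohort.

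**2. The protocol's own sample size**

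Inputs from Power Estimates: 0.15 against 0.30, alpha 0.05 (taken as two-sided), power 80%. With pooled variance and no continuity correction,

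n = [1.960·√(2·0.225·0.775) + 0.842·√(0.15·0.85 + 0.30·0.70)]² / 0.15² = (1.157 + 0.489)² / 0.0225 ≈ 120.5, so 121 per arm.

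This matches the stated figure. The present point does not change it.

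**3. Chance imbalance in a cohort of fixed size, unrestricted 1:1:1 allocation**

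The SD of an arm's count is √(N·⅓·⅔). The other figures come from 200,000 multinomial draws.

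| Cohort | Expected per arm | SD | Mean smallest arm | Mean gap, largest to smallest (95th percentile) |
|---|---|---|---|---|
| 250 | 83 | 7.5 | 76 | 15 (30) |
| 500 | 167 | 10.5 | 156 | 22 (43) |

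For 250, 83.3 ± 1.96·7.45 gives 69 to 98 per arm.

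**4. Cost in power**

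For 0.15 against 0.30, 83 per arm gives 64.1% and an illustrative split of 72 against 95 gives 62.5%. The loss is 1.6 points. (That 64.1% lies below 80% reflects the size of the cohort, not the allocation method.)

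**5. Cost in enrolment, one cohort**

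Assume per-arm targets of one third of the cohort. With unrestricted allocation, reaching 83 in every arm takes 273 patients on average (95th percentile 300), against 3·83 = 249 with perfect balance. Reaching 167 takes 534 (573), against 3·167 = 501.

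**6. Cost in enrolment, all cohorts together**

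Assumptions, none of them in the protocol:

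- Per-arm targets are 83 HFrEF, 83 HFpEF, 167 AF and 83 T2D/ASCVD.
- Patients are equally likely to have HFrEF, HFpEF or no HF. AF is present in half of those with HF and in all others. T2D/ASCVD is present in one third, independently. On average this mix gives the planned 250/250/500/250 per 750 patients.
- There are five sites (the protocol says 4-6).
- Targets for underserved groups are left out, because no numbers are given.

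| Recruitment | Allocation | Mean enrolled when the rule is met |
|---|---|---|
| Any eligible patient | simple | 871 |
| Any eligible patient | blocks by site | 854 |
| Any eligible patient | blocks by site and cohort | 804 |
| Only patients who fill an open cohort | blocks by site | 810 |
| Only patients who fill an open cohort | blocks by site and cohort | 777 |

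Savings from adding cohort: 871 − 804 = 67 against simple allocation; 854 − 804 = 50 against site blocks; 810 − 777 = 33 against site blocks with targeted recruitment. The range is therefore about 35 to 65. Excess over 750 that remains after the change: 804 − 750 = 54, or 777 − 750 = 27.

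**The case against.** The strongest reply is that this is mostly wording. The sentence on simple randomisation stands in a paragraph that argues for individual over cluster allocation, so simple may mean no more than individual-level. The item A heading and the power paragraph agree on site stratification. This is a fair reading, and it is why unrestricted allocation cannot be taken as the protocol's settled method. It does not remove the point. The term still names a different method, the item A text still stratifies only the analysis, and site stratification does not balance disease cohorts.

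It can also be said that the harm is small. The stopping rule sets a floor on each arm, the primary outcome is a change from baseline (which removes at least part of any difference in baseline level), and covariate adjustment may be left to the SAP. All of this stands, and it limits the size of the point.

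Some stronger readings are tempting but not supported:

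- A reader might infer a contradiction between "patient accrual in both disease categories" and the four cohorts of the Population section. The sentence goes on to the representation of underserved groups, so it reads naturally as joining two kinds of target. Even if it counts diseases, power is claimed for exactly two groups.
- A reader might blame the whole excess over 750 on simple allocation. Balanced allocation also exceeds 750 under the same assumptions.
- A reader might settle on a single saving of about 70 patients. That takes simple allocation as the comparator and ignores that the Randomization Scheme plans prospective identification of patients by disease state. With site blocks and targeted recruitment the saving is about half as large.
- A reader might conclude that arms will close short of patients. The fixed-cohort ranges in step 3 do not describe a trial that stays open until every arm meets its targets.

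**Conclusion.** The point holds as a matter of consistency and efficiency, not of validity. The protocol gives conflicting descriptions of the allocation method and credits a stratified analysis with producing balance. Under each description disease cohort is left out of the allocation, although the protocol's own stopping rule and power claims rest on it.

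Individual 1:1:1 randomisation gives a valid comparison either way, the stated 121 per arm is unaffected, and the power cost of chance imbalance is about 1 to 2 points. The main cost is avoidable enrolment of about 35 to 65 patients. That range depends on per-arm targets of one third of each cohort and on an assumed comorbidity mix. Whether there is any effect on a pooled outcome from unequal disease mix has not been quantified. The change is worth making because it is cheap and helps under every reading of the text.

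**What to change.** State one scheme in the same terms in the Randomization Scheme, item A of the site procedures, and Statistical Methods:

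- Individual-level 1:1:1 allocation in the existing software, balanced on site and main disease cohort (HFrEF / HFpEF / no HF; AF yes/no; T2D/ASCVD yes/no), by minimisation or by permuted blocks over a small number of strata.
- An analysis adjusted for the same factors.
- *Individual-level* in place of *simple (traditional)*.
- Deletion of the statement that stratifying the analysis ensures balance.

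The cost is a software setting, a small amount of set-up work and a few wording changes. Full cross-classified blocking should be avoided. The three disease factors give 3·2·2 − 1 = 11 possible patterns, since every patient has at least one condition. With five sites that makes 55 strata, and 750/55 ≈ 14 patients per stratum, or fewer than five per arm. This is why minimisation or a coarser set of strata is preferable. Writing the per-arm targets into the protocol would also let the team replace the assumed enrolment figures above with its own.

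### The bolded design row of the power table gives 424 per arm for 15% vs 30%, a size that belongs to 15% vs 22.5%, and so contradicts the claim that 121 per arm powers education vs decision support

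*Protocol*

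**What the plan says.** All the figures are in the protocol's Statistical Methods section, in the Power Estimates paragraph and the table below it.

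- **Control rate.** "Current estimates of use of either SGLT2i or GLP-1RA among eligible patients is 15" per cent.
- **Error rate.** "Assuming an alpha of 0.05"; sidedness is not stated.
- **Size and effect.** "we would require 121 patients in each of the 3 arms to show 80% power to detect at least an absolute difference of 15" percentage points. The text names both contrasts. For 1 vs 2 it specifies an "absolute difference of 15% between education alone and the education + decision support arms". For 1 vs 3 it sets the same 15 points.
- **Total.** "Assuming a 20-25% loss to follow-up rate, 750 patients would be required".
- **Allocation** (Research Methods, Randomization Scheme). "Patients will be randomized 1:1:1 to the 3 quality improvement strategies".
- **Role of the contrasts.** 1 vs 3 is primary and 1 vs 2 is secondary. The protocol says that the study has power for both, in T2D/ASCVD and in heart failure with the two types combined.
- **Bolded table row.** Rates 0.15 / 0.3 / 0.3. Patients per arm for 1 vs 2: 424 at 80% power and 568 at 90%. For 1 vs 3: 121 and 161.

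**The concern.** In the bolded row arms 2 and 3 have the same assumed rate, so 1 vs 2 and 1 vs 3 are the same calculation: 0.15 against 0.30, equal allocation, same alpha, same power. The row nevertheless asks for about 3.5 times as many patients for one as for the other (424/121). It also contradicts the text above it, which says that 121 per arm is enough for both.

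The other rows suggest how this arose. In each of them the arm 2 rate lies midway between arms 1 and 3 (0.075, 0.15, 0.1875). The same pattern would put 0.225 in the bolded row.

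This row carries the design assumption. If the rate behind 424 and 568 is the one the sponsor believes, the trial is far too small for the technology comparison while the protocol says it is powered. A null result for that arm could then be read as evidence that technology adds nothing to education, when the trial had little ability to show otherwise.

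**Working it through.** **Formula.** Pooled-variance comparison of two proportions, two-sided alpha 0.05, equal arms, no continuity correction:

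n per arm = [1.960·√(2p̄(1−p̄)) + z·√(p₁(1−p₁) + p₂(1−p₂))]² / (p₂−p₁)², rounded up, where p̄ is the mean of the two rates and z = 0.842 for 80% power or 1.282 for 90%.

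Two-sided testing is an assumption. It is supported by the next step.

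**Step 1: reproduce the rest of the table.** All 12 sizes in the first three rows come out exactly.

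| Rates (arms 1 / 2 / 3) | 1 vs 2, 80% | 1 vs 3, 80% | 1 vs 2, 90% | 1 vs 3, 90% |
|---|---|---|---|---|
| 0.05 / 0.075 / 0.10 | 1471 | 435 | 1969 | 582 |
| 0.10 / 0.15 / 0.20 | 686 | 199 | 918 | 266 |
| 0.125 / 0.1875 / 0.25 | 529 | 152 | 708 | 203 |

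**Step 2: bolded row as printed, 0.15 vs 0.30.** Here p̄ = 0.225, √(2·0.225·0.775) = 0.5906 and √(0.1275 + 0.2100) = 0.5809.

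- 80%: (1.1575 + 0.4889)² / 0.15² = 2.7106 / 0.0225 = 120.5, so **121**.
- 90%: (1.1575 + 0.7445)² / 0.0225 = 160.8, so **161**.

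These match the 1 vs 3 cells and not the 1 vs 2 cells.

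**Step 3: can another standard formula give 424 and 568 from 0.15 vs 0.30?** No.

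| Variant | 80% | 90% |
|---|---|---|
| One-sided 0.05 | 95 | 131 |
| Two-sided 0.025 | 147 | 191 |
| Two-sided 0.05, continuity-corrected | 134 | 174 |
| One-sided 0.05, continuity-corrected | 108 | 144 |
| Two-sided 0.025, continuity-corrected | 160 | 204 |
| Two-sided 0.05, unpooled variance | 118 | 158 |

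**Step 4: midpoint rate, 0.15 vs 0.225.** Here p̄ = 0.1875, √(2·0.1875·0.8125) = 0.5520 and √(0.1275 + 0.1744) = 0.5494.

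- 80%: (1.0819 + 0.4624)² / 0.075² = 2.3848 / 0.005625 = 423.97, so **424**.
- 90%: (1.0819 + 0.7041)² / 0.005625 = 567.07, so **568**.

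Both printed 1 vs 2 figures are matched exactly.

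**Step 5: power for 1 vs 2 under each reading.** Power = Φ[((p₂−p₁)√n − 1.960·√(2p̄(1−p̄))) / √(p₁(1−p₁) + p₂(1−p₂))]. For 0.15 vs 0.225 at n = 121: (0.075·11 − 1.0819) / 0.5494 = −0.468, which gives 32.0%.

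| Evaluable per arm | Basis | Arm 2 = 22.5% | Arm 2 = 30% |
|---|---|---|---|
| 121 | size in the text | 32% | 80% |
| 188-200 | all 750, 25-20% lost (250 × 0.75 to 250 × 0.80) | 46-48% | 94-95% |
| 250 | all 750, no loss | 57.5% | 98% |
| 63-67 | 250 T2D/ASCVD patients, 25-20% lost (83.3 × 0.75 to 83.3 × 0.80) | 19-20% | 52-55% |

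**Step 6: does the total of 750 settle which rate was meant?** No. Dividing by the retained fraction, 121 per arm needs 3 × 152 = 456 (20% loss) to 3 × 162 = 486 (25% loss). For 424 per arm the totals are 3 × 530 = 1,590 to 3 × 566 = 1,698. Neither is 750.

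**The case against.** The strongest reply is that the text is arithmetically right as written. It specifies 15 points for both contrasts, 121 per arm does give 80% power for that, and the printed arm 2 rate of 0.3 agrees. Only the two 1 vs 2 size cells disagree. They may be left over from a time when arm 2 was set at 22.5%, a rate that the protocol nowhere states. On that reading the correction is two cells and no power is lost. The primary comparison is unaffected either way.

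Much of this stands. The document does not show which entry is the error, so the low power figures apply only if 22.5% is the working assumption. The 63-67 per arm row of the power table mixes in a separate matter, the size of the T2D/ASCVD cohort, which leaves only 52-55% power even at 30%. It should not be charged to this row alone. How a null result would be reported is a risk, not something the protocol states. Equal rates in arms 2 and 3 are not an error in themselves, since the text gives a difference to detect and plans no 2 vs 3 test. They do depart, without explanation, from the graded rates in the other three rows.

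What does not stand is any suggestion that the row can be left alone. Its rates and sizes cannot both be right, and the text relies on one while the table prints the other.

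**Conclusion.** The concern holds. The 424 and 568 in the bolded row are not the sizes for the printed 0.15 vs 0.30; they are exactly those for 0.15 vs 0.225. One of two things is therefore wrong in the protocol:

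- **If arm 2 is 22.5%**, the statement that 121 per arm suffices for both contrasts and the claim of power for the secondary comparison are false. Power for 1 vs 2 is 32% at 121 per arm and at most 57.5% with all 750 patients and no loss. The comparison would need 3 × 424 = 1,272 evaluable patients, or about 1,590-1,698 enrolled.
- **If arm 2 is 30%**, the cells should read 121 and 161, and the text is arithmetically correct at 121 per arm.

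The result rests on two-sided 0.05 and the pooled formula, which reproduce every other cell. The 1 vs 3 figures are correct as printed.

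**What to change.** State which arm 2 rate is the design assumption and make the row, the text and the power claim agree.

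- **If 0.225:** print 0.225 with 424/568 and limit the 121-per-arm statement to 1 vs 3. Withdraw the claim that 1 vs 2 is powered and give its actual power (32% at 121 evaluable per arm). Presenting 1 vs 2 as estimation, with a confidence interval, would make its status plain; restating the power is the minimum.
- **If 0.30:** replace 424/568 by 121/161 and add a sentence on why arms 2 and 3 are given the same rate when the other rows are graded.

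In either case, state that alpha is two-sided.

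The cost is one or two table cells and a few sentences. Under the first option a stated power claim is given up. Neither option changes enrolment, data collection or the primary comparison.

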### *Type 2 Diabetes Mellitus (T2D)*

Over 34 million Americans have T2D and >7 million have established cardiovascular disease. T2D is associated with diminished life expectancy (by up to 6-7 years for an average 60-year-old patient).

Patients with T2D have traditionally been managed with diet/lifestyle optimization, glycemic control, other risk factor control (including of blood pressure, weight, and smoking cessation), statin therapy, and renin-angiotensin-system inhibitors (in select patients). The SGLT2i and the GLP-1RA are 2 classes of antihyperglycemic therapies that have demonstrated clinically important improvements in cardiovascular, kidney, and mortality outcomes among high-risk patients with T2D. Despite their availability and a strong evidentiary base, their uptake in clinical practice remains suboptimal. Even with expanding insurance coverage and accruing clinical practice guideline support (across specialties), recent national data have suggested that only ~10-15% of eligible patients are on 1 of these risk reduction therapies. Innovative strategies are needed to promote optimal care practices among high-risk patients living with T2D.

We designed the TRANSFORM as a US-based multi-center trial with the goal of defining optimal implementation strategies to integrate GDMT across disease states, especially in underserved populations or those with health care disparities historically. The study was designed specifically to capture patients across broad integrated health systems encountering multiple

clinician types. All quality improvement initiatives will be remotely deployed directly to clinicians caring for eligible patients by trained Study Managers.

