**Population:**

**750 total with comorbidity overlap (250 HFrEF, 250 HFpEF, 500 AF, 250 T2D/ASVD)**

*Inclusion criteria:*

1. Age  $\geq 18$  years
2. Personal access to a computer and/or smartphone for app download
3. Heart Failure (reduced and preserved ejection fraction) AND/OR
4. Atrial Fibrillation with CHA2DS2-VASc score greater than or equal to 2 in men and greater than or equal to 3 in women AND/OR
5. T2D and ASCVD, defined as follows:
  - a. Known CAD, prior ACS, or coronary artery revascularization
  - b. Prior TIA/stroke or known carotid or intracerebral atherosclerosis
  - c. Prior PAD including requiring revascularization

*Exclusion criteria:*

- All patients
  - Current or anticipated participation in an interventional clinical trial of a drug/device
  - Currently receiving comfort care or enrolled in hospice
  - Life expectancy <1 year
  - Pregnancy or active breastfeeding
  - Current or anticipated participation in an interventional clinical trial (other than TRANSFORM GDMT)
  - Patients without a clinical encounter within three years of study start date
- Heart Failure patients:
  - History of or plan for heart transplantation or left ventricular assist device
  - Palliative chronic inotropic therapy
  - NYHA Class 4 heart failure
- Atrial Fibrillation patients:
  - Current prescription for OAC
  - Reversible cause of atrial fibrillation, such as post-cardiothoracic surgery or thyrotoxicosis
  - History of ischemic stroke in prior 7 days
  - Transient ischemic attack in prior 3 days
  - Platelet count <70,000/ml
  - Hemoglobin concentration <8g/dl
  - History of or condition associated with increased bleeding risk, such as hemophilia
  - History of mechanical valve replacement
  - Major surgical procedure or trauma within 14 days
  - Clinically significant gastrointestinal bleeding within 8 weeks

- History of intracranial, intraocular, spinal, or atraumatic intra-articular bleeding
- T2D/ASCVD patients with or without HF or AF:
  - Current prescription for SGLT2i and GLP-1RA
  - Current or planned hemodialysis
  - Decompensated end stage liver disease
  - Type 1 diabetes
  - Prior diabetic ketoacidosis
  - Gestational diabetes
  - History of pancreatitis or pancreatic cancer

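### The total of 750 patients does not follow from 121 per arm with 20-25% loss, which gives 454-484; the real basis of 750 is not stated.

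*Protocol*

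**What the plan says.** All inputs are in the protocol.

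- **Control rate** (Statistical Methods, Power Estimates): "Current estimates of use of either SGLT2i or GLP-1RA among eligible patients is 15" per cent.
- **Effect** (same paragraph): "to detect at least an absolute difference of 15% between education alone and the education + decision support arms", with the same 15-point difference for education alone against the referral arm.
- **Size per arm** (same paragraph): "Assuming an alpha of 0.05, we would require 121 patients in each of the 3 arms to show 80% power".
- **Total** (the sentence that follows): "Assuming a 20-25% loss to follow-up rate, 750 patients would be required".
- **Allocation** (Research Methods, Randomization Scheme): "Patients will be randomized 1:1:1 to the 3 quality improvement strategies".
- **Population** (Study Design): "750 total with comorbidity overlap", made up of 250 HFrEF, 250 HFpEF, 500 AF and 250 T2D/ASCVD. Patient Recruitment gives the same figures.

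The bold row of the sample size table also shows 121 for arm 1 vs arm 3 at 80% power. The same section says that the study will be powered for T2D/ASCVD and for HF (HFrEF and HFpEF combined), and that it does not expect to reach power for AF.

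**The concern.** The two sentences read as one derivation: a number per arm, three arms, an allowance for loss, then a total. No step is given in between, and the wording makes 750 the number that the calculation calls for. It is not. The trial's headline sample size is therefore justified by a calculation that does not produce it.

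Two things are at stake. First, nobody can check the design, because the consideration that really set 750 is not on the page. Second, a total well above the calculated need makes the plan look amply sized. Yet the rates in the calculation belong to T2D/ASCVD patients, who are only a third of the planned total (250 of 750).

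**Working it through.** **Inputs.** p1 = 0.15, p2 = 0.30, alpha 0.05, power 80%, three equal arms and loss d = 20-25%, all from Power Estimates and the Randomization Scheme. The protocol does not say whether alpha is one- or two-sided. Two-sided is taken here because it reproduces the plan's own figure.

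**Step 1: reproduce 121.** The pooled-variance formula for two proportions, without continuity correction, is

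n = [z(0.975)·√(2·p̄·(1−p̄)) + z(0.80)·√(p1(1−p1) + p2(1−p2))]² / (p2−p1)²

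With p̄ = 0.225:

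- first term: 1.960 × √0.34875 = 1.1575
- second term: 0.8416 × √0.3375 = 0.4889
- n = 1.6464² / 0.0225 = 120.5, so 121 per arm.

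This matches the text and the table. The same formula gives 161 at 90% power, also a match, so the method is not in doubt.

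**Step 2: go from 121 to the total.**

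- Evaluable: 3 × 121 = 363.
- 20% loss: 363 / 0.80 = 453.75, so 454.
- 25% loss: 363 / 0.75 = 484.
- Stated: 750. Excess: 750 − 484 = 266 (55%) to 750 − 454 = 296 (65%).
- Loss that would turn 363 into 750: 1 − 363/750 = 51.6%.

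**Step 3: try other conventions, keeping 15% vs 30% and alpha 0.05.**

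| Variant | Total at 20-25% loss |
|---|---|
| As stated | 454-484 |
| Inflating by N × (1 + d) | 436-454 |
| One-sided alpha 0.05 | 357-380 |
| Continuity correction (134 per arm) | 503-536 |
| 90% power (161 per arm) | 604-644 |
| 90% power with continuity correction (174 per arm) | 653-696 |

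None reaches 750. The bold row's arm 1 vs arm 2 figure of 424 does not help either, since 3 × 424 = 1,272 already exceeds 750 before any loss. (That figure fits 15% vs 22.5%, not the 30% printed beside it, which is a separate matter.)

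**Step 4: power that the planned numbers give for 15% vs 30%.**

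Power = Φ{[0.15·√n − 1.960·√0.34875] / √0.3375}

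| Population | Evaluable per arm | Power |
|---|---|---|
| 250 T2D/ASCVD, 20% loss | 250/3 × 0.80 = 66.7 | 54.6% |
| 250 T2D/ASCVD, 25% loss | 250/3 × 0.75 = 62.5 | 51.9% |
| All 750, 20% loss | 250 × 0.80 = 200 | 95.1% |
| All 750, 25% loss | 250 × 0.75 = 187.5 | 93.9% |

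The last two rows hold only if 15% and 30% apply to every patient, whatever the disease. To have 121 evaluable per arm within T2D/ASCVD, the 454-484 of Step 2 would have to be T2D/ASCVD patients.

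**The case against.** The strongest reply is that nothing is lost. Read as an all-patient comparison at 15% vs 30%, 750 is more than enough. The Randomization Scheme also ends enrolment on arm targets by disease category and on representation of underserved groups, so the sentence does not by itself drive accrual. That stands, and it limits the consequence. It does not repair the sentence, which presents 750 as the result of a calculation that gives 454-484.

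The 80% power is also attached to 121 per arm and not to 750. The protocol does not claim that 750 patients give 80% power, and it should not be read as if it did. Nor is the design row unclear, since the text and the bold row both name 15% vs 30%.

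A reader might infer where 750 came from. Two inferences are tempting, and the protocol supports neither.

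- **The 10% vs 20% row.** At 80% power it needs 199 per arm, and 3 × 199 / 0.80 = 746. But 597 / 0.75 = 796 at the other end of the stated loss range. Other routes also come close. 12.5% vs 25% at 90% power (203 per arm) gives 609 / 0.80 = 761. 15% vs 30% with two-sided alpha 0.025 and 90% power (191 per arm) gives 573 / 0.80 to 573 / 0.75 = 717-764. With several near matches, none is evidence. The background statement that "only ~10-15% of eligible patients are on 1 of these risk reduction therapies" describes national uptake and does not show a 10% design rate.
- **The disease targets.** They add to 250 + 250 + 500 + 250 = 1,250, not 750. With HFrEF and HFpEF taken as mutually exclusive, overlap allows any total from 500 to 1,250. The Population section states 750 alongside the targets and derives nothing.

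**Conclusion.** The point holds as an error of derivation. From the stated inputs the requirement is 363 evaluable and 454-484 randomised. The stated 750 is 55-65% higher, would need 51.6% loss, and has no stated basis.

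It does not follow that the trial as a whole is underpowered. If the 15% and 30% rates applied to all 750 patients, power would be about 94-95%. For the group that the 15% rate describes, the picture is different: 250 planned T2D/ASCVD patients give about 83 per arm, 63-67 after loss, and about 52-55% power for 15% vs 30%. That does not agree with the statement that the study is powered for T2D/ASCVD.

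These figures assume two-sided alpha 0.05, the pooled two-proportion formula, an even split of the T2D/ASCVD patients across arms, the stated loss in every arm, and that 250 is the full T2D/ASCVD count including patients with overlapping conditions. If more are enrolled, power in that group rises.

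**What to change.** In Power Estimates:

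1. Replace the sentence on the total so that the 15% vs 30% calculation ends in 363 evaluable patients, and 454-484 randomised at 20-25% loss.
2. Have the sponsor state what actually set 750, without presenting it as the result of this calculation. The reason should come from the sponsor's records and not be fitted to a table row or to the disease targets afterwards.
3. State the power for 15% vs 30% in the 250 planned T2D/ASCVD patients (about 52-55% after loss), and bring the statement that the study is powered for that group into line with it.
4. If an all-patient power is also given (94-95% at 188-200 per arm), label it as assuming that the 15% and 30% rates apply to all 750 patients.

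The cost is rewording one paragraph. Correcting the sentence requires no change in enrolment. Whether to enlarge the T2D/ASCVD target is a separate decision, which the sponsor can take once the figures are stated correctly.
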